2.4.3 SPECIAL NOTES ON RESPONSE ASSESSMENT

When nodal disease is included in the sum of target lesions and the nodes decrease to ‘normal’ size (< 10 mm), they may still have a measurement reported on scans. This measurement should be recorded even though the nodes are normal in order not to overstate progression should it be based on increase in size of the nodes. As noted earlier, this means that patients with CR may not have a total sum of ‘zero’ on the case report form (CRF).

Patients with a global deterioration of health status requiring discontinuation of treatment without objective evidence of disease progression at that time should be reported as ‘symptomatic deterioration’. Every effort should be made to document objective progression even after discontinuation of treatment. Symptomatic deterioration is not a descriptor of an objective response: it is a reason for stopping study therapy. The objective response status of such patients is to be determined by evaluation of target and non-target disease as shown in Tables A-C.

For equivocal findings of progression (e.g. very small and uncertain new lesions; cystic changes or necrosis in existing lesions), treatment may continue until the next scheduled assessment. If at the next scheduled assessment, progression is confirmed, the date of progression should be the earlier date when progression was suspected.

In studies where patients with advanced disease are eligible (i.e. primary disease still or partially present), the primary tumor should be also captured under target or non-target lesions as appropriate. This is to avoid wrong assessments of complete overall response by statistical programs while the primary is still present but not evaluable.

**19.5 APPENDIX 5 - INTERNATIONAL MYELOMA WORKING GROUP (IMWG)
UNIFORM RESPONSE AND RELAPSE CRITERIA FOR MULTIPLE
MYELOMA**

Response	IMWG criteria ²
sCR ²	CR as defined below plus: 
○ Normal FLC ratio and○ Absence of clonal cells in bone marrow³ by immunohistochemistry or immunofluorescence⁴
CR ²	Negative immunofixation on the serum and urine and disappearance of any soft tissue plasmacytomas and ≤ 5% plasma cells in bone marrow ³
VGPR ^{2,5}	Serum and urine M-protein detectable by immunofixation but not on electrophoresis or ≥ 90% or reduction in serum M-protein plus urine M-protein level < 100 mg per 24 hour
PR ^{2,5}	
≥ 50% reduction of serum M-protein and reduction in 24-hour urinary M-protein by ≥ 90% or to < 200 mg per 24 hours
 
If the serum and urine M-protein are unmeasurable, a ≥ 50% decrease in the difference between involved and unininvolved FLC levels is required in place of the M-protein criteria
 
If serum and urine M-protein are not measurable, and serum free light assay is also not measurable, ≥ 50% reduction in plasma cells is required in place of M-protein, provided baseline bone marrow plasma cell percentage was ≥ 30%
 
In addition to the above listed criteria, if present at baseline, a ≥ 50% reduction in the size of soft tissue plasmacytomas is also required

MR	NA
No change / SD	Not meeting criteria for CR, VGPR, PR or progressive disease
Plateau	NA
Relapse	
Progressive disease ⁶	
Increase of ≥ 25% from lowest response value in any one or more of the following:
 
 ○ Serum M-component and/or (the absolute increase must be ≥ 0.5 g/dL)⁷ ○ Urine M-component and/or (the absolute increase must be ≥ 200 mg per 24 hours) ○ Only in patients without measurable serum and urine M-protein levels, the difference between involved and unininvolved FLC levels. The absolute increase must be > 10 mg/dL ○ Bone marrow plasma cell percentage. The absolute percentage must be ≥ 10%⁸ ○ Definite development of new bone lesions or soft tissue plasmacytomas or definite increase in the size of existing bone lesions or soft tissue plasmacytomas

	IMWG criteria ²
Response	
	
 ○ Development of hypercalcemia (corrected serum calcium > 11.5 mg/dL or 2.65 mmol/L) that can be attributed solely to the plasma cell proliferative disorder
Relapse ⁶	
Clinical relapse requires one or more of:
 
Direct indicators of increasing disease and/or end organ dysfunction (CRAB features).⁷ It is not used in calculation of time to progression or progression-free survival but is listed here as something that can be reported optionally or for use in clinical practice.
 
 1. Development of new soft tissue plasmacytomas or bone lesions 2. Definite increase in the size of existing plasmacytomas or bone lesions. A definite increase is defined as a 50% (and at least 1 cm) increase as measured serially by the sum of the products of the cross-diameters of the measurable lesion 3. Hypercalcemia (> 11.5 mg/dL) (2.65 mmol/L) 4. Decrease in hemoglobin of ≥ 2 g/dL (1.25 mmol/L) 5. Rise in serum creatinine by 2 mg/dL or more (177 μmol/L or more)
Relapse from CR ⁶ (to be used only if the end point studied is DFS) ⁹	
Any one or more of the following:
 
 ○ Reappearance of serum or urine M-protein by immunofixation or electrophoresis ○ Development of $\geq 5\%$ plasma cells in the bone marrow⁸ ○ Appearance of any other sign of progression (i.e., new plasmacytoma, lytic bone lesion, or hypercalcemia)

CR, complete response; DFS, disease-free survival; FLC, free light chain; PR, partial response; SD, stable disease; sCR, stringent complete response; VGPR, very good partial response.

1. Adapted from Durie BGM, et al. Leukemia 2006;20:1467-1473; and Kyle RA, Rajkumar SV. Leukemia 2008;23:3-9.
2. All response categories require two consecutive assessments made at any time before the institution of any new therapy; all categories also require no known evidence of progressive or new bone lesions if radiographic studies were performed. Radiographic studies are not required to satisfy these response requirements.
3. Confirmation with repeat bone marrow biopsy not needed.
4. Presence/absence of clonal cells is based upon the kappa/lambda ratio. An abnormal kappa/lambda ratio by immunohistochemistry and/or immunofluorescence requires a minimum of 100 plasma cells for analysis. An abnormal ratio reflecting presence of an abnormal clone is kappa/lambda of $> 4:1$ or $< 1:2$.
5. A clarification to IMWG criteria for coding CR and VGPR in patients in whom the only measurable disease is by serum FLC levels: CR in such patients is defined as a normal FLC ratio of 0.26–1.65 in addition to CR criteria listed above. VGPR in such patients is defined as a $> 90\%$ decrease in the difference between involved and uninvolved free light chain (FLC) levels.
6. All relapse categories require two consecutive assessments made at any time before classification as relapse or disease progression and/or the institution of any new therapy. In the IMWG criteria, CR patients must also meet the criteria for progressive disease shown here to be classified as progressive disease for the purposes of calculating time to progression and progression-free survival. The definitions of relapse,

clinical relapse and relapse from CR are not to be used in calculation of time to progression or progression-free survival.

7. For progressive disease, serum M-component increases of ≥ 1 gm/dL are sufficient to define relapse if starting M-component is ≥ 5 g/dL.
8. Relapse from CR has the 5% cut-off versus 10% for other categories of relapse.
9. For purposes of calculating time to progression and progression-free survival, CR patients should also be evaluated using criteria listed above for progressive disease.

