3.3 CENTRES

This study is a multinational, multicentre study conducted in 6 countries and approximately 30 sites.

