7.2.3 Laboratory Test Abnormalities

Local laboratories will be used for all laboratory tests. Laboratory test results will be recorded on the laboratory results form of the eCRF.

Any laboratory result abnormality fulfilling the criteria for a serious adverse event (SAE) should be reported as such, in addition to being recorded as an AE in the eCRF.

Any treatment-emergent abnormal laboratory result that is clinically significant, i.e., meeting one or more of the following conditions, should be recorded as a single diagnosis on the adverse event page in the eCRF:

- Is accompanied by clinical symptoms
- Leading to a change in study medication (e.g. dose modification, interruption or permanent discontinuation)
- Results in a medical intervention (e.g., potassium supplementation for hypokalaemia) or a change in concomitant therapy
- Is clinically significant in the investigator's judgment

Note: For oncology trials, certain abnormal values may not qualify as adverse events.

It is the investigator's responsibility to review all laboratory findings. Medical and scientific judgment should be exercised in deciding whether an isolated laboratory abnormality should be classified as an adverse event.

If a clinically significant laboratory abnormality is a sign of a disease or syndrome (e.g., alkaline phosphatase and bilirubin $5 \times$ ULN associated with cholestasis), only the diagnosis (i.e., cholestasis) should be recorded on the Adverse Event eCRF.

If a clinically significant laboratory abnormality is not a sign of a disease or syndrome, the abnormality itself should be recorded on the Adverse Event eCRF, along with a descriptor indicating if the test result is above or below the normal range (e.g., "elevated potassium," as opposed to "abnormal potassium"). If the laboratory abnormality can be characterized by a precise clinical term per standard definitions, the clinical term should be recorded as the adverse event. For example, an elevated serum potassium level of 7.0 mEq/L should be recorded as "hyperkalaemia."

Observations of the same clinically significant laboratory abnormality from visit to visit should only be recorded once on the Adverse Event eCRF (see [Section 7.3.2](#) for details on recording persistent adverse events).

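### Appendix 5 gives the myeloma hypercalcaemia limit for progression as 11.5 mg/dL or 2.65 mmol/L, which are different concentrations, and does not say which governs

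*Protocol*

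**What the plan says.** Section 5.3.6.2 sends the assessment of myeloma response to Appendix 5 (Section 19.5). In the progressive disease row of that table, any one of several items is enough. The last item is "Development of hypercalcemia (corrected serum calcium > 11.5 mg/dL or 2.65 mmol/L"), which counts only if the plasma cell disorder is its sole explanation.

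The clinical relapse row prints the same pair with the second figure in brackets, in the manner of a conversion: "Hypercalcemia (> 11.5 mg/dL) (2.65 mmol/L"). That row says of itself that it is optional and does not enter time to progression (TTP) or progression-free survival (PFS).

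Two other items in the relapse row also carry two units: "Rise in serum creatinine by 2 mg/dL or more (177 μmol/L or more") and "Decrease in hemoglobin of ≥ 2 g/dL (1.25 mmol/L").

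Two footnotes to the table govern how progression is used. Footnote 6: "All relapse categories require two consecutive assessments made at any time before classification as relapse or disease progression". Footnote 9, on TTP and PFS: "CR patients should also be evaluated using criteria listed above for progressive disease".

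On where calcium is measured, Section 7.2.3 says "Local laboratories will be used for all laboratory tests", and Section 3.3 says "This study is a multinational, multicentre study conducted in 6 countries and approximately 30 sites". Section 5.4.1 places calcium in the routine biochemistry panel.

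**The concern.** A limit printed in two units should be one concentration. If it is not, a patient whose value falls between the two has progressed by one figure and not by the other, and the protocol offers no rule for choosing.

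The progressive disease row is operative. By Section 8.1.2, the date of progression ends TTP, PFS and duration of response. By Sections 3.1 and 6.2, investigator-assessed progression is also a reason to stop treatment. An ambiguous limit therefore touches three secondary endpoints and one treatment decision in Cohort 6.

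**Working it through.** **Inputs**

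| Quantity | Value | Source |
|---|---|---|
| Calcium limit, conventional unit | 11.5 mg/dL | Appendix 5, progressive disease and clinical relapse rows |
| Calcium limit, SI unit | 2.65 mmol/L | same rows |
| Molar mass of calcium | 40.078 g/mol (range tried 40.0 to 40.1) | physical constant, not in the protocol; assumed |
| Creatinine pair | 2 mg/dL, 177 μmol/L | Appendix 5, clinical relapse row |
| Haemoglobin pair | 2 g/dL, 1.25 mmol/L | Appendix 5, clinical relapse row |

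**Step 1. Try to reproduce the printed SI figure.** mmol/L = (mg/dL × 10) / molar mass.

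11.5 × 10 / 40.078 = 2.869, that is 2.87 mmol/L (2.868 to 2.875 over the range). The printed 2.65 is not reproduced. The rounded factor 0.25 gives 11.5 × 0.25 = 2.875. Milliequivalents give 2 × 2.869 = 5.74 mEq/L. Neither is 2.65.

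**Step 2. Convert in the other direction.** mg/dL = mmol/L × molar mass / 10.

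2.65 × 40.078 / 10 = 10.62 mg/dL (10.60 to 10.63 over the range), against the printed 11.5.

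**Step 3. Could rounding explain it?** The pair would agree only if the molar mass were 115 / 2.65 = 43.4 g/mol. The relative gap is 2.869 / 2.65 − 1 = 8.3%. Rounding does not account for that.

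**Step 4. Check the neighbouring pairs in the same way.**

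- Creatinine (molar mass 113.12 g/mol, assumed): 20 mg/L / 113.12 × 1000 = 176.8 μmol/L, printed as 177.
- Haemoglobin (monomer, 16.114 g/mmol, assumed): 20 g/L / 16.114 = 1.24 mmol/L, printed as 1.25.

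Both agree to within rounding or nearly so. Of the pairs checked, only calcium is at fault, in both rows.

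**Step 5. Width of the disputed band.** 2.87 − 2.65 = 0.22 mmol/L, or 11.50 − 10.62 = 0.88 mg/dL. Values inside and outside it:

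| Corrected calcium, mmol/L | Same value, mg/dL | Above 2.65 mmol/L? | Above 11.5 mg/dL? |
|---|---|---|---|
| 2.60 | 10.42 | no | no |
| 2.70 | 10.82 | yes | no |
| 2.75 | 11.02 | yes | no |
| 2.85 | 11.42 | yes | no |
| 2.90 | 11.62 | yes | yes |

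The SI figure is the lower limit, so applying it can only call progression at the same time or earlier.

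**Step 6. Does any reading of the text remove the problem?**

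- The two figures are meant as equivalents, as the bracketed form in the relapse row suggests. They are not equivalent.
- Either figure suffices. Then 11.5 mg/dL does no work, because every value above it is already above 2.65 mmol/L. The rule would be uniform, but one of its two numbers would be redundant.
- Each laboratory's result is compared with the figure in its own unit. Then classification inside the band depends on the reporting unit.

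The text does not choose among these.

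**The case against.** The strongest reply is that the reach is narrow, and most of it stands.

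- **Attribution and confirmation.** The hypercalcaemia must have no cause other than the plasma cell disorder, and footnote 6 asks for two consecutive assessments. A single reading inside the band is not progression under either figure. These conditions reduce the number of cases, but they do not settle a case that meets both.
- **Only one of the two rows affects analysis.** The clinical relapse row is excluded from TTP and PFS. It should be corrected for consistency, not because it changes a result.
- **One cohort and secondary endpoints.** Only Cohort 6 uses these criteria, and Section 8.3.2 summarises the time-to-event endpoints by Kaplan-Meier estimates with confidence intervals.
- **Corrected calcium is not a routine panel result.** Section 5.4.1 lists calcium but not albumin; albumin appears among the myeloma assessments in footnote 16 of Table 8a. Calcium being drawn regularly therefore does not show that a corrected value exists at every visit.
- **Possible inheritance.** The appendix says it is adapted from published criteria, which are not at hand, so whether the pair was copied or mistyped cannot be checked. The appendix is the rule for this trial either way.

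Three stronger readings are tempting, and the documents do not support them.

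- A reader might infer that the same patient is progressed in one country and a responder in another. Local laboratories in 6 countries make mixed units possible, but the protocol does not state which unit any site reports or applies, and on the either-suffices reading the rule is the same everywhere.
- A reader might infer that the Week 8 response rate is distorted. The partial response row carries no calcium condition, footnote 2 bars response only where bone lesions are known to be new or progressing, and Section 8.1.1 defines myeloma responders by response category. Nothing says how a patient who meets both partial response and the calcium item is scored.
- A reader might go on to infer a loss of power for the two-stage rule. That would require assuming both an affected patient and the unproven effect on response, so a power figure would not measure this defect. The title of Table 16 also excepts Cohort 6, although its body says all cohorts and Table 15 gives myeloma the same sample sizes.

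**Conclusion.** The point holds in a limited form. The calcium pair in Appendix 5 is wrong as written: its two figures differ by 0.22 mmol/L (0.88 mg/dL, 8.3%), and no reading of the text makes both serve as the limit. A corrected calcium above 2.65 and up to 2.87 mmol/L that satisfies the attribution and confirmation conditions can be progression or not according to the figure used. The consequence that the text supports is for TTP, PFS, duration of response and stopping for progression in the myeloma cohort.

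The arithmetic is certain apart from the assumed molar mass, which changes only the third significant figure. The number of patients in the band cannot be derived from the protocol; given the narrow band, the two conditions and the single cohort, it is probably small. No effect on the primary endpoint is shown.

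**What to change.** In the progressive disease row and the clinical relapse row of Appendix 5, make the two calcium figures the same concentration. If 11.5 mg/dL is meant, its equivalent is 2.87 mmol/L; if 2.65 mmol/L is meant, its equivalent is 10.62 mg/dL. Which limit is intended is for the sponsor to decide; this review does not choose. Add one sentence saying that this single limit applies at all sites, with local results converted to the reference unit before comparison.

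The cost is one corrected number in each of two table rows and one added sentence. No further data, visits or tests are needed.

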APPENDIX 6 - ECOG PERFORMANCE STATUS SCALE

Grade	Description
0	Fully active, able to carry on all pre-disease performance without restriction
1	Restricted in physically strenuous activity but ambulatory and able to carry out work of a light or sedentary nature, e.g., light housework or office work
2	Ambulatory and capable of all self-care but unable to carry out any work activities. Up and about > 50% of waking hours
3	Capable of only limited self-care, confined to a bed or chair > 50% of waking hours
4	Completely disabled. Cannot carry on any self-care. Totally confined to bed or chair
5	Dead

**19.7 APPENDIX 7 - NATIONAL CANCER INSTITUTE-COMMON TOXICITY
CRITERIA FOR ADVERSE EVENTS, V4.0**

The Common Terminology Criteria for Adverse Events v4.0, updated June 14, 2010, is available at: <http://evs.nci.nih.gov/ftp1/CTCAE/About.html>

19.8

APPENDIX 8 - ICH GUIDELINES FOR CLINICAL SAFETY DATA MANAGEMENT, DEFINITIONS, AND STANDARDS FOR EXPEDITED REPORTING, TOPIC E2

A serious adverse event is any experience that suggests a significant hazard, contraindication, side effect or precaution. It is any AE that at any dose fulfils at least one of the following criteria:

- is fatal (i.e., the adverse event actually causes or leads to death); (results in **death**; NOTE: death is an outcome, not an event)
- is Life-Threatening (i.e., the adverse event, in the view of the investigator, places the patient at immediate risk of death)

This does not include any adverse event that had it occurred in a more severe form or was allowed to continue might have caused death.

- required in-patient hospitalization or prolongation of existing hospitalization;
- results in persistent or significant disability/incapacity (i.e., the adverse event results in substantial disruption of the patient's ability to conduct normal life functions);
- is a congenital anomaly/birth defect in a neonate/infant born to a mother exposed to study drug;
- is medically significant in the investigator's judgment (e.g., may jeopardize the patient or may require medical/surgical intervention to prevent one of the outcomes listed above)

Medical and scientific judgment should be exercised in deciding whether expedited reporting to the Sponsor is appropriate in other situations, such as important medical events that may not be immediately life-threatening or result in death or hospitalization but may jeopardize the patient or may require intervention to prevent one of the outcomes listed in the definitions above. These situations should also usually be considered serious.

Examples of such events are intensive treatment in an emergency room or at home for allergic bronchospasm; blood dyscrasias or convulsions that do not result in hospitalization; or development of drug dependency or drug abuse.

An unexpected AE is one, the nature or severity of which is not consistent with the applicable product information.

Causality is initially assessed by the Investigator. For Serious Adverse Events, possible causes of the event **are** indicated by selecting one or more options. (Check all that apply)

- Pre-existing/Underlying disease - specify
- Study treatment – specify the drug(s) related to the event
- Other treatment (concomitant or previous) – specify
- Protocol-related procedure
- Other (e.g. accident, new or intercurrent illness) - specify

The term severe is a measure of intensity, thus a severe AE is not necessarily serious. For example, nausea of several hours' duration may be rated as severe, but may not be clinically serious.

A serious adverse event occurring during the study or which comes to the attention of the Investigator within 15 days after stopping the treatment or during the protocol-defined follow-up

period, if this is longer, whether considered treatment-related or not, must be reported. In addition, a serious adverse event that occurs after this time, if considered related to test “drug”, should be reported.

Such preliminary reports will be followed by detailed descriptions later which will include copies of hospital case reports, autopsy reports and other documents when requested and applicable.

For serious adverse events, the following must be assessed and recorded on the AEs page of the eCRF: intensity, relationship to test substance, action taken, and outcome to date.

The Investigator must notify the Ethics Review Committee/Institutional Review Board of a serious adverse event in writing as soon as is practical and in accordance with international and local laws and regulations.

ROCHE LOCAL COUNTRY CONTACT for SAEs: Local Monitor

The local Monitor will be the initial point of contact for all study related issues. The local monitor is responsible to provide administrative details and contact information of the Roche study team as required.

ROCHE HEADQUARTERS CONTACT for SAEs and other medical emergencies: Clinical Operations

The local Monitor will be the initial point of contact for all study related issues. The local monitor is responsible to provide administrative details and contact information of the Roche study team as required.

c. 24-HOUR MEDICAL COVERAGE

To ensure the safety of study patients, an Emergency Medical Call Center Help Desk will access the Roche Medical Emergency List, escalate emergency medical calls, provide medical translation service (if necessary), connect the investigator with a Roche Medical Monitor, and track all calls. The Emergency Medical Call Center Help Desk will be available 24 hours per day, 7 days per week. Toll-free numbers for the Help Desk, as well as Medical Monitor contact information, will be distributed to all Investigators.

19.9 APPENDIX 9 - ADDITIONAL GUIDANCE FOR PATIENTS WITH PROSTATE CANCER INCLUDED IN COHORT 7 (OTHER TUMOURS)

Cohort 7 (Other solid tumours) may include prostate cancer patients. For these patients, the following prostate specific eligibility criteria will be used. These will only apply to patients with prostate cancer and are in addition to the main study criteria for solid tumours.

Additional inclusion criteria for patients with prostate cancer:

1. Patients with measurable and non-measurable disease according to RECIST v1.1, for soft tissue lesions and/or according to the Prostate Cancer Clinical Trials Working Group 2 (PCWG2) for bone lesions are eligible
2. Evidence of progressive metastatic disease since the most recent change of therapy as assessed by the investigator with the following:
 - Increasing serum prostate specific antigen (PSA) levels, the most recent value \geq 2 ng/mL. (Increasing levels must be confirmed by 3 consecutive PSA measurements, preferably with 14 days, but with at least 7 days between each measurement.)
 - Progression of soft tissue metastasis (computed tomography [CT] scan or magnetic resonance imaging [MRI] according to RECIST v1.1)
 - Progression of bone disease (at least 1 new bone lesion as measured by bone scan)

Additional exclusion criteria for patients with prostate cancer:

1. Prostate cancer pain that warrants the initiation of radio- or chemotherapy.
2. Concurrent administration of any anti-cancer therapies (e.g., radiotherapy, chemotherapy, other targeted therapy, vaccines, antiandrogens, experimental drug, etc.) other than those administered in this study. In patients with prostate cancer, ongoing treatment with luteinizing hormone-releasing hormone (LHRH) agonists or antagonists, denosumab (Prolia) or bisphosphonate (e.g., zoledronic acid) is allowed. At the discretion of the investigator, castrate resistant prostate cancer (CRPC) patients receiving gonadotropin-releasing hormone agonist therapy or bisphosphonate (e.g., zoledronic acid) may have that treatment continued while they are enrolled in this study.

Duration of treatment:

Vemurafenib will be given until the development of progressive disease (as per Investigator assessment), unacceptable toxicity, withdrawal of consent, protocol violation endangering the patient's safety, death, reasons deemed critical by the treating physician, or study termination by the Sponsor, however a minimum of 16 weeks treatment will be given to allow sufficient time to assess any response in prostate cancer as per the PCWG2 guidelines.

Additional assessments for patients with prostate cancer:

- Tumour assessment will be performed at 8-weekly intervals according to the Response Evaluation Criteria In Solid Tumours (RECIST v1.1), for soft tissue lesions and/or the PCWG2 for bone lesions³

- PSA levels will be measured every 8 weeks and monitored according to the PCWG2 guidance for PSA³.

PCWG2 guidance for bone lesions³

Assessment of bone lesions will be based on radionuclide scans. The outcome of bone scans should be recorded as either new lesions or no new lesions. If there are new lesions present on cycle 3, Day 1 (the first scan) then a confirmatory scan should be performed 8 weeks later. If new lesions are confirmed at Cycle 5 Day 1 reassessment then this is defined as disease progression according to PCWG2. For subsequent scans from Cycle 5 Day 1 onwards, any new bone lesions present are defined as disease progression according to PCWG2.

PCWG2 guidance for PSA³

A PSA progression is defined as the time from start of therapy to first PSA increase that is $\geq 25\%$ and ≥ 2 ng/mL above the nadir, and which is confirmed by a second PSA value 4 weeks later (i.e., a confirmed rising trend)

APPENDICES References

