5.3.6 Response Criteria

5.3.6.1 Solid tumours

Response of measurable solid tumours to study treatment will be evaluated by the Investigator according to RECIST, v1.1 criteria ([Appendix 4](#)) (67). See [Appendix 9](#) for prostate, [Appendix 10](#) for ECD and/or LCH specific response criteria.

Tumour evaluations will occur once during the Screening Period (Days –28 and –1), every 8 weeks after starting vemurafenib during the Treatment Period, and at the End of Treatment Visit. A window of \pm 5 days of scheduled visit is allowed to complete the tumour assessments at the required intervals.

Radiological tumour assessments to measure extent of disease will be carried out by CT/MRI of the chest/abdomen/pelvis (C/A/P) for all patients. In addition, CT/MRI of the brain can be performed if clinically indicated and as per standard care.

Patients should be assessed at the designated time points using a consistent imaging modality. The same imaging technique must be used for a patient throughout the study. The same method of assessment and the same technique should be used to characterize each identified and reported lesion at baseline and during follow-up. If more than one method of assessment is used at baseline, the most accurate method according to RECIST should be selected when recording data; in addition, this method should be performed in all subsequent evaluations. Tumour measurements should be made by the same Investigator/radiologist for each patient during the study to the extent that this is feasible.

For solid tumours to be assigned a status of partial response (PR) or complete response (CR) (i.e., a responder), changes in tumour measurements must be confirmed by repeat assessments performed no less than 4 weeks after the criteria for response are first met, i.e., patients need to have two consecutive assessments of PR or CR to be a responder.

Symptomatic deterioration may indicate progressive disease (PD). However, radiological confirmation of PD is strongly recommended.

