2.3.1 EVALUATION OF TARGET LESIONS

Complete Response (CR): Disappearance of all target lesions. Any pathological lymph nodes (whether target or non-target) must have reduction in short axis to $<$ 10 mm.

Partial Response (PR): At least a 30% decrease in the sum of diameters of target lesions, taking as reference the baseline sum diameters.

Progressive Disease (PD): At least a 20% increase in the sum of diameters of target lesions, taking as reference the smallest sum on study including baseline (nadir). In addition to the relative increase of 20%, the sum must also demonstrate an absolute increase of at least 5 mm. (Note: the appearance of one or more new lesions is also considered progression).

Stable Disease (SD): Neither sufficient shrinkage to qualify for PR nor sufficient increase to qualify for PD.

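### Appendix 9's unqualified 16-week treatment minimum for prostate patients, read literally, keeps vemurafenib going after clear RECIST soft-tissue progression at Week 8 (minor)

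*Protocol*

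**What the plan says.** Protocol Appendix 9 (Section 19.9), under its heading on duration of treatment, starts with the usual stopping list: "Vemurafenib will be given until the development of progressive disease (as per Investigator assessment), unacceptable toxicity, withdrawal of consent", and further reasons that include those the treating physician considers critical. The same sentence then turns with a 'however' and states that "a minimum of 16 weeks treatment will be given to allow sufficient time to assess any response in prostate cancer as per the PCWG2 guidelines". No exception follows.

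Appendix 9 sets three ways of following disease:

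- Soft tissue: "Tumour assessment will be performed at 8-weekly intervals according to the Response Evaluation Criteria In Solid Tumours (RECIST v1.1), for soft tissue lesions".
- Bone: new lesions on the first scan, at Cycle 3 Day 1, need a second scan 8 weeks later. "If new lesions are confirmed at Cycle 5 Day 1 reassessment then this is defined as disease progression according to PCWG2".
- PSA: a rise counts once a second value 4 weeks later confirms it.

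Soft-tissue disease is expected in these patients. The entry evidence of progressive disease includes "Progression of soft tissue metastasis (computed tomography [CT] scan or magnetic resonance imaging [MRI] according to RECIST v1.1").

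Appendix 4 defines target-lesion progression as "At least a 20% increase in the sum of diameters of target lesions, taking as reference the smallest sum on study", together with an absolute increase of at least 5 mm; a new lesion also counts. Only for equivocal findings does Appendix 4 (2.4.3) say that "treatment may continue until the next scheduled assessment".

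Sections 3.1 and 6.2 allow treatment after progression as an option, for patients who in the Investigator's opinion would still benefit, once the Sponsor has been consulted. Section 3.1 includes the special one-year option for ECD/LCH but does not mention a minimum for prostate cancer.

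**The concern.** One sentence gives sites two instructions that cannot both be followed when soft-tissue disease clearly progresses at the first on-treatment scan: stop at progression, and treat for 16 weeks.

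Patient care is at stake, not inference. A site that follows the minimum literally keeps dosing a patient whose disease has clearly grown, without the benefit judgement and Sponsor consultation that Sections 3.1 and 6.2 attach to treatment past progression. Other anti-cancer therapy is excluded while the patient is on study (Section 4.4.1.1), so any next treatment would also wait, if there is one. A site that stops must rely on general discretion to set aside a duration that Appendix 9 says will be given.

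**Working it through.** The protocol gives no figure to reproduce here. The check is a comparison of the rules, plus calendar arithmetic.

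**Inputs**

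- Cycle length: 28 days (Section 3.1).
- First on-treatment soft-tissue scan: Week 8, Cycle 3 Day 1 (Appendix 9; Table 8a).
- Treatment minimum: 16 weeks (Appendix 9).
- Scan window: plus or minus "5 days of scheduled visit is allowed to complete the tumour assessments at the required intervals" (Section 5.3.6.1).
- Dose: 960 mg twice daily (Section 6.2).

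**Calendar**

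- Cycle 3 Day 1 = 2 × 28 + 1 = Day 57, after 8 completed weeks.
- Cycle 5 Day 1 = 4 × 28 + 1 = Day 113, after 112 / 7 = 16 completed weeks.
- Extra treatment after progression at Day 57: 113 − 57 = 56 days.
- Scan 5 days early (Day 52): 113 − 52 = 61 days. Scan 5 days late (Day 62): 113 − 62 = 51 days.
- Scheduled doses: 56 × 2 = 112, range 51 × 2 = 102 to 61 × 2 = 122. At full dose 56 × 1.92 g = 107.5 g; an interruption or reduction would lower this.

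**When each type of progression can first be established, against the Week 16 minimum**

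| Site of disease | Rule | Earliest point | Before Week 16? |
|---|---|---|---|
| Bone | New lesions at Cycle 3 Day 1, confirmed at Cycle 5 Day 1 | Week 16 | No |
| PSA | Rise at Week 8, confirmed 4 weeks later | Week 8 + 4 = Week 12 | Yes |
| Soft tissue, clear | RECIST v1.1, single assessment | Week 8 | Yes |

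The 16 weeks coincide exactly with the bone confirmation scan, so for bone the minimum and the progression rule agree. For soft tissue they are 8 weeks apart, and no exception bridges the gap. For PSA they are 4 weeks apart, so the requirement to confirm a PSA rise does not close that gap either. A repaired clause has to name PSA.

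**The parallel appendix.** Appendix 10 uses the same bone-scan rule for ECD/LCH. It deals with early bone-scan change narrowly: such change before Cycle 5 may not be the only evidence of progression. It sets no minimum duration, and RECIST progression remains a reason to stop.

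**The case against.** The best defence is that the protocol leaves ways out. Section 4.5 lets the Investigator withdraw a patient for treatment failure or in the patient's best interest, and the Appendix 9 sentence itself lists reasons the treating physician considers critical. An investigator can therefore stop at Day 57 within the protocol. This stands, and it rules out a stronger reading that a reader might infer: that stopping at progression is necessarily a departure from the protocol. It does not remove the conflict, because those exits are general and the sentence still directs 16 weeks.

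A second defence is that a duration with a floor is a coherent, tumour-specific design choice. That is possible. But a deliberate floor would require drug after clear progression, which Sections 3.1 and 6.2 make optional and conditional, and no text gives Appendix 9 precedence on duration.

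Third, the stated purpose is to assess any response under the PCWG2 guidelines, which need not mean bone alone. Whether the cited guideline supports treating through early soft-tissue change cannot be checked from the protocol. The PCWG2 guidance that Appendix 9 reproduces covers bone and PSA only; for soft tissue it names RECIST v1.1.

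A reader might also infer that the clause overrides unacceptable toxicity, the QTc rules or withdrawal of consent. The documents do not support that: Sections 4.5, 6.2.1 and 11.2.1 apply to all patients. The wording is loose on these items too, but the separate rules govern.

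Finally, harm from a delayed next therapy is uncertain. Eligibility (Section 4.2) requires disease that is refractory to standard therapy, or for which such therapy does not exist or is not considered appropriate; and patients may leave the study at any time.

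**Conclusion.** The point holds as a minor correction. Read literally, Appendix 9 tells sites to give about 8 more weeks of vemurafenib (56 days, range 51 to 61) after clear soft-tissue progression at Week 8. This conflicts with the progression stopping reason in the same sentence and with the conditional option in Sections 3.1 and 6.2.

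The day count assumes progression declared at the first scheduled scan and treatment taken to exactly 16 weeks; the dose count also assumes no interruption. Only Cohort 7 prostate patients with such progression are affected. The protocol gives no number for them, and there may be none, since Appendix 9 says only that Cohort 7 may include prostate patients. The Week 8 response is already determined by then, and no endpoint, sample size or error rate changes.

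**What to change.** In Appendix 9, delete the clause that sets the 16-week minimum and replace it with a narrow rule on the Appendix 10 pattern, for example:

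> *Before Cycle 5 Day 1 (approximately 16 weeks), new bone lesions not yet confirmed under the PCWG2 rule below, and PSA rises, are not sufficient on their own to declare progression. Soft-tissue progression by RECIST v1.1 and all other listed stopping reasons apply at any time. Treatment past progression remains possible after discussion with the Sponsor (Section 3.1).*

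The text should name PSA and soft tissue explicitly. A general exception for any other listed stopping reason would be circular, because progression is itself on that list.

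The cost is one clause in one appendix. No visit, scan, endpoint or sample size changes, and the protection against stopping too early on a bone scan is kept.
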